Secondary Study Objectives	
The secondary objectives of this study are to:
 
 1) Compare total plaque volumes per-patient and per lesion as well as comparing different plaque type volumes to the IVUS reference standard and assess reproducibility of quantitative plaque measurements compared to the reference standard. 2) Perform exploratory analyses on plaque in previously stented vessels (protocol to allow up to 20% (50 patients) with one or two stented vessels vessels in this category. This can also include plaque proximal or distal to the stented vessel.
Hypotheses	The primary hypothesis of the study is that a deep-learning based automated method for segmenting coronary atherosclerotic plaques can quantify total plaque volume from CCTA with an acceptable level of agreement with IVUS measurements. The secondary hypothesis of the study is that CCTA-derived coronary models can accurately assess percent plaque burden as well as calcified, low attenuation, and fibrous plaque volumes with an acceptable level of agreement and repeatability compared to IVUS.
Population	Clinically stable patients with known CAD who have a CCTA showing stenosis in at least one major epicardial vessel of stentable/graftable diameter and in whom clinically-indicated IVUS is planned.
Study Design and Methods	This is a prospective, multi-center study. All patients who have a stenosis in at least one major epicardial vessel confirmed by CCTA, who have undergone FFR _{CT} analysis, and who are scheduled to undergo clinically indicated IVUS-guided invasive evaluation and/or treatment will be eligible for enrollment. Enrolling sites will have FFR _{CT} analysis incorporated when indicated into their standard evaluation of CCTA scans. Data collected will include CCTA and FFR _{CT} , full angiographic, and IVUS images, and if obtained, any other imaging or physiologic data including OCT, FFR, any NHPR (e.g., dPR, RFR, iFR, etc.), and pre-

REVEALPLAQUE Study Protocol Version 1.0 August 12th, 2021

	
and post-stent implantation invasive data. All non-invasive and invasive data collected will be obtained as clinical practice consistent with standard clinical care.
 
All details about cardiovascular testing and treatment (planned and actual) will be recorded at baseline. There will be no study required visits after the baseline invasive procedure.

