Subjects included in the study will have anatomic and physiological data obtained as standard clinical care during ICA recorded. A guide advising how to obtain IVUS measurements will be provided to sites during site protocol training; in summary the below mentioned data will be collected. A maximum of 20% of enrolled subjects may have at least one vessel with prior stent implantation.

ICA procedure:

1. The subject's vital signs (blood pressure and heart rate) will be recorded prior to ICA procedure.
2. Medications (adenosine and nitrates) taken within 24 hours of ICA will be recorded.
3. Angiography is advised to be performed according to the study guides provided during site protocol training.
4. The data from IVUS (mandatory), FFR measurements (as deemed necessary), and OCT (as deemed necessary) by the physician will be collected.
5. All angiographic images will be collected.
6. IVUS data for non-targeted lesions that are standard clinical care will be collected.
7. Radiation exposure will be documented.
8. Total procedural volume of iodinated contrast will be recorded
9. Fluoroscopy duration will be documented.
10. Diagnostic and therapeutic procedures and equipment used, including catheters, balloons, wires, and stents, and vessels treated will be documented.

REVEALPLAQUE Study Protocol Version 1.0 August 12th, 2021

11. Procedural complications will be documented (e.g., dissection from catheter or wire, reaction to medication, side branch occlusion, slow/no flow)

V. E. Follow up

No follow up with the subjects will be done as a part of this study.

VI. STUDY DURATION

The anticipated enrollment duration of the REVEALPLAQUE study will be approximately 12 months. No subject follow up is planned for this study.

VI. A. Rules for Subject Withdrawal

Each subject is free to withdraw from the study at any time. No additional data will be collected after a subject informs the Investigator that they want to withdraw. Withdrawn subjects will be considered screen failures if the collected data does not allow for adequate selection criteria assessment.

VI. B. Screen Failures

Subjects who sign consent will be deemed a screen failure if:

- Automatic pullback for IVUS catheter was not used during the procedure
- Prior to IVUS, the vessel was predilated (medications OK)

No data beyond reason for screen failure will be collected.

VI. C. Rules for Terminating the Study

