The REVEALPLAQUE study is a prospective study which collects data from clinically indicated CCTA imaging and ICA procedures. These procedures will have been planned as part of routine clinical practice; therefore, no additional clinical risks are related to participating in the study. Procedural complications will be documented that are related to IVUS or FFR (e.g., dissection from catheter or wire, reaction to medication).

IX. STATISTICAL CONSIDERATIONS**IX. A. General Considerations**

Descriptive statistical methods will be used to summarize the data from this study, with confidence intervals and hypothesis testing performed for the primary and other selected efficacy endpoints. Unless stated otherwise, the term “descriptive statistics” refers to number of events (n), mean, median, standard deviation (SD), standard error, minimum, maximum, and coefficient of variation (CV) for continuous data and frequencies and percentages for categorical data.

All data collected during the study will be included in data listings.

Unless specified otherwise, all statistical testing will be two-sided and will be performed using an overall significance (alpha) level of 0.05.

All statistical analyses will be conducted with the SAS® System, version 9.1.3 or higher.

A statistical analysis plan (SAP) will describe the methods of data collection, validation, analysis, and reporting. The sections below provide a brief overview of statistical consideration for the study.

IX. B. Subject Characteristics

Subject accountability will be described, including number of subjects enrolled, number of subjects included in the analysis, and reasons for any subjects discontinued from the study or not included in the analysis. Demographic information will be summarized using descriptive statistics. Sex and medical histories will be summarized by counts and percentages.

IX. C. Endpoint Analysis

The primary endpoint is to assess the level of agreement between total plaque volume of a deep-learning based automated method for segmenting coronary atherosclerotic plaques, compared to IVUS, on a per-IVUS-pullback level.

Bland Altman plots will be constructed. If the deep-learning based automated method CCTA measurements fall with the limits of agreement (LoA) estimated from the IVUS measurements, the

REVEALPLAQUE Study Protocol Version 1.0 August 12th, 2021

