measures will be assumed to agree. Additionally, Pearson's correlation and paired t-test will be constructed to further describe the relationship between IVUS measurements and deep-learning based automated method for segmenting coronary atherosclerotic plaques from CCTA.

All secondary endpoints which are continuous (e.g., per lesion total plaque volume, per lesion calcium volume, per lesion low attenuation volume, per lesion non-calcified plaque volume, segment involvement score) will be similarly compared using a Bland Altman plot, Pearson's correlation and paired t-tests. Reproducibility will be estimated with Intra Class correlation (ICC).

IX. D. Sample Size

Approximately 250 subjects may be enrolled into this study.

From published data (Conte 2019), the maximum allowable difference between the measurements is 36 mm³. Assuming a standard deviation of 12 mm³, a sample size of 223 patients achieves 90% power to detect agreement when the mean is 8, confidence level of the (LoA) is 0.950 and the confidence level of the confidence intervals about the LoA is 0.950.

IX. E. Analysis Populations

All subjects who meet the study criteria, sign the written informed consent, and are enrolled in the study, and provide paired assessments of CCTA and IVUS measurements will be included in the analysis set.

X. DATA HANDLING AND QUALITY ASSURANCE

X. A. Completing and Signing Case Report Forms

This study will utilize eCRFs for the collection of all data. Data changes and corrections for any errors should be corrected within the eCRF. The audit trail will record all changes made, the date and time of the correction, the person making the change, and a reason for the change. The appropriate electronic signature will be provided by the investigator as indicated.

X. B. Clinical Data Management

The sponsor or designee will be responsible for the processing and quality control of the data. The handling of data, including data quality control, will comply with all applicable regulatory guidelines.

The training of clinical site personnel in eCRF completion will be the responsibility of the sponsor or designee. To ensure uniform data collection, Case Report Form Guidelines will be created to assist with eCRF completion. All site staff including investigators and research coordinators will undergo site initiation training to become thoroughly familiar with the protocol, case report forms, and with methods of data verification.

X. C. Archiving of Data

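### Secondary endpoints: the only significance test named has a zero-difference null and ignores patient clustering; report bias and limits of agreement with patient-clustered 95% CIs instead

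*Combined protocol and SAP*

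**What the plan says.** The secondary hypothesis (Study Synopsis, Hypotheses) is that the CCTA models can assess "percent plaque burden as well as calcified, low attenuation, and fibrous plaque volumes with an acceptable level of agreement" and repeatability against IVUS.

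Section IX.C states that the continuous secondary endpoints "will be similarly compared using a Bland Altman plot", followed by Pearson's "correlation and paired t-tests. Reproducibility will be estimated with Intra Class correlation (ICC"). The ICC is tied to reproducibility. In the primary-endpoint paragraph of the same section, Pearson's "correlation and paired t-test will be constructed to further describe the relationship between IVUS measurements" and the automated CCTA method, so there the two statistics supplement the Bland-Altman analysis.

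The secondary endpoints in section III.B are defined per pullback and per lesion. Section V.D adds that "IVUS data for non-targeted lesions that are standard clinical care will be collected". Section IX.A provides for confidence intervals and "hypothesis testing performed for the primary and other selected efficacy endpoints", without naming the others. It also announces a separate SAP: "The sections below provide a brief overview of statistical consideration for the study". That SAP is not among the documents.

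The only allowable difference in the documents is 36 mm³, in section IX.D, for total plaque volume.

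**The concern.** The hypothesis concerns acceptable agreement, but the one significance test named in IX.C has a null of zero mean difference. Rejecting that null does not show disagreement of any practical size, and failing to reject it does not show agreement. The test does not assess the width of the differences. For a given bias, it penalises a precise method and favours a noisy one. Pearson's r does not change when one method is shifted or rescaled by a positive factor, so it measures association.

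The ordinary paired t-test also treats all pairs as independent. Where a patient contributes several lesions or pullbacks and the differences are positively correlated within patient, its standard error is too small. IX.C names no method that allows for this.

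What is at stake is how the secondary results are read. Most of these endpoints have no allowable difference, so the p-value and r are the figures most easily taken as a verdict.

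**Working it through.** **Inputs from section IX.D:** mean difference 8 mm³, SD 12 mm³, n = 223 patients, allowable difference 36 mm³, LoA level 0.95, level of the CIs about the LoA 0.95. **From IX.A:** two-sided alpha 0.05. **Assumed, because the documents give no figure:** number of lesions per patient and within-patient correlation (ICC) of the differences.

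**1. The plan's sample size.** Agreement is taken to require that the 95% CIs of both LoA lie within ±36, with SE(LoA) = SD × √(1/n + 1.96²/(2(n-1))) and non-central t power. This gives n = 223 with power 0.900, so the stated figure reproduces.

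**2. LoA at the planning values.**
- LoA = 8 ± 1.96 × 12 = -15.5 and 31.5 mm³.
- SE(LoA) = 12 × √(1/223 + 3.84/444) = 1.375; half-width of the CI = 1.971 × 1.375 = 2.71.
- Outer bounds: -15.52 - 2.71 = -18.2 and 31.52 + 2.71 = 34.2. Both are inside ±36.

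**3. Paired t-test at the same values.**
- SE of the bias = 12/√223 = 0.804; t = 8/0.804 = 9.96; two-sided p = 1.5e-19.
- 95% CI of the bias = 8 ± 1.971 × 0.804 = 6.4 to 9.6 mm³.

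So the scenario for which the plan claims "90% power to detect agreement when the mean is 8" is also one in which the t-test reports an overwhelming difference. With 223 independent pairs, any observed bias above 1.971/√223 = 0.13 SD of the differences is significant; at SD 12 that is about 1.6 mm³.

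**4. The reverse case.** With a true bias of zero, the test is non-significant in 95% of studies by construction, for any SD. For illustration, at an assumed SD of 60 mm³ the LoA are ±1.96 × 60 = ±118 mm³, and the t-test is still non-significant 95% of the time.

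**5. Clustering.** Let DE be the design effect for the mean difference. The naive standard error is too small by a factor √DE, and the true two-sided error is about 2 × (1 - Φ(1.96/√DE)).

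If every patient gives k lesions, DE = 1 + (k-1) × ICC. If a fraction f of patients gives a second lesion and the rest give one, DE = 1 + 2f × ICC/(1+f).

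| Assumption | DE | True SE / naive SE | False-positive rate |
|---|---|---|---|
| f = 10%, ICC 0.1 | 1.018 | 1.01 | 5.2% |
| f = 20%, ICC 0.5 | 1.167 | 1.08 | 7.0% |
| all give 2, ICC 0.1 | 1.1 | 1.05 | 6.2% |
| all give 3, ICC 0.5 | 2.0 | 1.41 | 16.6% |

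Intervals suffer in the same way. In simulation with 223 patients, 2-3 lesions each and ICC 0.1-0.5, naive 95% CIs for the bias covered about 83-94% and those for the upper LoA about 86-94%. Cluster-robust intervals covered about 94-96%.

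**The case against.** The strongest reply is that the plan does not rest agreement on these statistics. Bland-Altman is the lead method for the secondary endpoints too and would display wide limits. For the primary endpoint, r and the t-test are expressly supplementary, and the word similarly can be read as carrying that role over. This stands. A reader might infer that the plan uses a p-value or r to declare acceptable agreement; nothing in the documents says so.

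Second, section IX is an overview and the SAP is to give the methods. Silence on clustering or on CIs therefore does not show that they are unplanned. That is fair, but IX.C does name the paired t-test, and an SAP that follows it would carry the test forward.

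Third, a reader might infer that no secondary endpoint has an allowable difference. That goes too far: per-pullback total plaque volume is listed as secondary and is the same quantity as the primary, to which 36 mm³ applies. The statement holds for the others.

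Fourth, the size is uncertain. The 223 independent pairs are the primary's patient count, and no lesion counts are given. Non-target IVUS is collected only where it is standard care, so the 6-17% error range cannot be presented as expected. If few patients give a second lesion, the effect is small.

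Fifth, a CI for the bias contains the same zero-null information as the t-test, and no interval can establish acceptability without a limit. Both are true. The gain is that the size of the bias and the spread are reported with their uncertainty, and the wording of the conclusion must follow.

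Finally, a concordance coefficient is largely a matter of preference: at bias 8 and SD 12, with an assumed IVUS volume SD of 50-100 mm³, r is 0.97-0.99 and concordance 0.96-0.99.

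**Conclusion.** The point holds as a correction to the supporting and secondary statistics. The zero-null paired t-test does not test the secondary hypothesis and, at the plan's own planning values, contradicts the plan's agreement result (p = 1.5e-19 beside LoA bounds of -18.2 and 34.2 mm³, inside ±36). That contrast uses only the figures in IX.D and one pair per patient.

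The clustering part is right in direction whenever patients give several positively correlated pairs. Its size rests on assumptions: a false-positive rate of about 5.2-7.0% if 10-20% of patients give a second lesion, and 6-17% if all give two or three, both with ICC 0.1-0.5.

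A reader might go further and infer that the primary conclusion or the sample size is undermined. The documents do not support that: the t-test has no part in the sample-size calculation, which reproduces, or in the primary agreement rule, which is stated in terms of LoA.

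**What to change.** In the SAP, for the continuous secondary endpoints and for the supporting statistics of the primary:

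- Replace the zero-null paired t-test p-value with the mean bias and the LoA, each with a 95% CI that allows for several pullbacks or lesions per patient, for example through a patient random effect or a patient-level bootstrap.
- Where no allowable difference is pre-stated, report the result as an estimate and not as proof of acceptable agreement. The 36 mm³ limit serves per-pullback total plaque volume; it cannot be carried over to endpoints on another scale, such as percent plaque burden, minimum lumen area or percentage area stenosis.
- Optionally, and as support only, add a concordance correlation or absolute-agreement ICC for CCTA against IVUS, read beside the LoA because it depends on the spread of values. If Pearson's r is kept, label it as association.

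The cost is SAP wording, minor programming on the same data and somewhat wider intervals. The primary decision rule, the sample size and the conduct of the study do not change.

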1. Compare total plaque volumes per-patient and per lesion as well as comparing different plaque type volumes to the IVUS reference standard and assess reproducibility of quantitative plaque measurements compared to the reference standard.
2. Perform exploratory analyses on plaque in previously stented vessels (protocol to allow up to 20% (50 patients) with one or two stented vessels in this category). This can also include

REVEALPLAQUE Study Protocol Version 1.0 August 12th, 2021

plaque proximal or distal to the stented vessel.

III. STUDY ENDPOINTS

III. A. Primary Endpoint

The primary endpoint is to assess the level of agreement between total plaque volume of a deep-learning based automated method for segmenting coronary atherosclerotic plaques, compared to IVUS, on a per-IVUS-pullback level.

III. B. Secondary Endpoints

Key secondary endpoints are:

Per pullback:

- Total plaque volume
- Percent plaque burden
- Calcified plaque volume
- Low attenuation plaque volume
- Fibrous plaque volume
- Segment involvement score (SIS)
- Adverse plaque characteristics (APC)

Per lesion:

- Total plaque volume
- Percent Plaque burden
- Calcified plaque volume
- Low attenuation plaque volume
- Fibrous plaque volume
- Minimum lumen area (MLA)
- Percentage area stenosis (%AS)
- Positive remodeling index

Per lesion/pullback:

- Reproducibility of all metrics above when quantified from different CCTA series
- Reproducibility of all metrics above when processing the same series twice (analyst and process variation)
- Exploratory analysis of necrotic core volume

IV. STUDY DESIGN

The REVEALPLAQUE study is a prospective, multi-center study designed to evaluate a deep-learning based automated method for segmenting coronary atherosclerotic plaques. All patients who have a stenosis confirmed by CCTA and FFR_{CT} available and who are scheduled to undergo IVUS will be eligible for enrollment. Enrolling sites will have FFR_{CT} analysis incorporated when indicated into their standard evaluation of CCTA scans. All sites will provide CCTA and FFR_{CT} images, full angiographic images, IVUS images, and if obtained, any other imaging or physiologic data including OCT, FFR, any NHPR (e.g., dPR, RFR, iFR, etc.), and pre- and post-stent implantation invasive data. All non-invasive and invasive data collected will be obtained as clinical practice consistent with standard clinical care.

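### ICC is the only statistic named for reproducibility, and alone it cannot show the repeat error of CCTA plaque volumes in mm³

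*Combined protocol and SAP*

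**What the plan says.** Section III.B (Secondary Endpoints) and the synopsis list two reproducibility endpoints for the per-lesion and per-pullback metrics: "Reproducibility of all metrics above when quantified from different CCTA series" and "Reproducibility of all metrics above when processing the same series twice (analyst and process variation".

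Section IX.C (Endpoint Analysis) deals with them in one sentence: "Reproducibility will be estimated with Intra Class correlation (ICC". It gives no form of ICC, no confidence interval and no acceptance limit. No within-subject SD, repeatability coefficient, within-subject CV or limits of agreement between repeats is named. The sentence before it says that continuous secondary endpoints "will be similarly compared using a Bland Altman plot, Pearson's correlation and paired t-tests". This follows the description of the primary CCTA-IVUS comparison.

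The synopsis (Hypotheses) states the secondary hypothesis for plaque burden and component volumes as accuracy "with an acceptable level of agreement and repeatability compared to IVUS". No number is attached to acceptable.

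Section IX.D (Sample Size) gives the only error figures in mm³, and these are for CCTA against IVUS: "the maximum allowable difference between the measurements is 36 mm³", "Assuming a standard deviation of 12 mm³", and "power to detect agreement when the mean is 8". Section IX.A describes the statistical section as an overview and leaves detail to a SAP. The supplied text contains no separate SAP.

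**The concern.** An ICC is the share of total variance that comes from true differences between the units measured, here lesions or pullbacks. Two studies with the same repeat error can report very different ICCs because their plaque volumes are more or less spread out. A high ICC may reflect a wide case mix, and a low one a narrow case mix.

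Two consequences follow. First, a user of the software needs to know how far two readings of the same plaque may differ, and an ICC without the between-subject spread does not say. Second, the plan will report an ICC for each of several volumes. Total, calcified and low attenuation volume may have quite different spreads, so ranking their repeatability by ICC would mix measurement error with case mix. The claim of acceptable repeatability in the secondary hypothesis would then rest on a figure that does not measure the error.

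**Working it through.** **The plan's own figure.** Section IX.D gives 223 patients for 90% power, with limit 36 mm³, mean 8, SD 12 mm³ (taken as the SD of CCTA-IVUS differences), 95% limits of agreement and 95% CIs about them.

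- SE of a limit = SD·√(1/n + 1.96²/(2(n−1))) = 12·√(1/223 + 3.8416/444) = 1.375 mm³.
- Upper limit = 8 + 1.96·12 = 31.52. Its upper 95% bound is 31.52 + 1.971·1.375 = 34.23, inside 36.
- Non-central t power is 0.8991 at n = 222 and 0.9004 at n = 223, so 223 is reproduced.

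This calculation concerns CCTA against IVUS. The plan states no figure for reproducibility.

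**Inputs for the reproducibility check.** Let sw be the within-subject SD (repeat readings of the same lesion or pullback) and sb the between-subject SD (spread across lesions or pullbacks). The documents give neither, so both are assumed. For sw I take 12 mm³. If CCTA and IVUS errors are independent, then SD² of the CCTA-IVUS differences = sw² + IVUS error variance. The plan's SD of 12 therefore implies that sw is at most 12.

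**Formulas**, with no systematic shift between repeats:

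- ICC = sb² / (sb² + sw²)
- Repeatability coefficient (RC) = 1.96·√2·sw

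**Results at sw = 12.** RC = 1.96·1.414·12 = 33.3 mm³ in every row.

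| sb (mm³) | ICC | RC (mm³) |
|---|---|---|
| 10 | 100/244 = 0.41 | 33 |
| 30 | 900/1044 = 0.86 | 33 |
| 60 | 3600/3744 = 0.96 | 33 |
| 100 | 10000/10144 = 0.99 | 33 |

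**A smaller error.** If the plan's variance of 144 is split equally between CCTA and IVUS, sw = 12/√2 = 8.49 and RC = 23.5 mm³. The ICC is then 0.58, 0.90, 0.97 and 0.99 at sb of 10, 25, 50 and 100 mm³. The pattern is the same.

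**The other direction.** Fix the ICC at 0.90 (a benchmark of mine, not the plan's). Then sw = sb·√(0.1/0.9) = sb/3. At sb = 25 this gives sw = 8.3 and RC = 23 mm³; at sb = 36 it gives sw = 12 and RC = 33 mm³. The same ICC therefore covers both. At sb = 50 it would correspond to sw = 16.7 and RC = 46 mm³, but that sw exceeds what the plan's SD of 12 allows under independent errors.

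**Check by simulation.** With 223 replicate pairs, sw = 12.99 and 1000 runs per setting, the mean ICC was 0.786, 0.937, 0.983 and 0.992 at sb of 25, 50, 100 and 150 mm³. The repeat limits stayed at about ±36 mm³ throughout. The formula gives 0.787, 0.937, 0.983 and 0.993.

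**The case against.** Several objections have force.

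- **Bland-Altman may already cover repeats.** Reproducibility is listed among the secondary endpoints, and the sentence before the ICC sentence covers all continuous ones. This reading is possible but weaker: that sentence points back to the IVUS comparison, and reproducibility then gets its own sentence with ICC only. If replicate plots were intended, one clause would settle it.
- **The SAP may specify it.** Section IX.A allows for that. If a SAP already names these statistics, the point is met. The text supplied does not show it.
- **The primary comparison would expose a large repeat error in total plaque volume.** This stands. With sw = 18, the CCTA-IVUS limits would be at least ±35.3 mm³. At n = 223 the upper bound would be 39.3 with no bias and 47.3 with the planned mean of 8, both beyond 36. But that comparison does not separate CCTA repeat error from IVUS error, and the plan states no limit for the component volumes.
- **A single RC in mm³ assumes constant error.** This also stands. If error grows with volume, the RC depends on case mix too, so the fix must allow for it.

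A reader might also infer more than the documents support:

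- *That the ICC will be near 1 whatever the error.* It is 0.41 in the first row of the table, and no spread is given.
- *That reproducibility faces a pass mark.* The plan only estimates it.
- *That lesions and pullbacks are pooled.* Section III.B lists separate per-lesion and per-pullback metrics, and the joint heading for reproducibility does not say that they are combined.
- *That the RC should be held to 36 mm³.* That limit was set for the CCTA-IVUS difference.
- *That CCTA cannot agree with IVUS better than with itself.* Two CCTA readings differ with variance 2·sw², but CCTA and IVUS differ with variance sw² plus IVUS error variance. With sw = 12 and error-free IVUS, the limits against IVUS are ±23.5 mm³, while the RC is 33.3 mm³.

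**Conclusion.** The point holds as a low-cost improvement to a secondary analysis. ICC is the only statistic named for the two reproducibility endpoints, and it cannot by itself show the repeat error in mm³ or be compared across plaque components. At a fixed RC of 33 mm³ it runs from 0.41 to 0.99 as the between-subject SD goes from 10 to 100 mm³.

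This rests on assumed SDs. The documents give neither a within-subject nor a between-subject SD; the value of 12 is the largest that fits the plan's own SD under independent errors. A misleading ICC, in either direction, is therefore shown to be possible, not certain. The primary endpoint and its sample size are not affected.

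**What to change.** In section IX.C, or in the SAP to which it defers, for each continuous volume metric and both reproducibility endpoints:

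- Report the within-subject SD and the repeatability coefficient (1.96·√2·within-subject SD), each with a 95% CI, and a Bland-Altman plot of the replicate pairs.
- Check whether the error grows with volume. If it does, use a within-subject CV or a log-scale version.
- Account in the CIs for several lesions or pullbacks from one patient.
- Keep the ICC beside these, stating its form (two-way, absolute agreement, single measurement) and its 95% CI.
- Do not use 36 mm³ as a pass mark for repeats.

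The cost is a few sentences of plan text, a little more analysis of the same replicate data, and the check for error that grows with volume. No further patients or readings are needed, and the 223-patient calculation is unchanged.
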